1.15 Premature discontinuation of treatment

The treatment may be discontinued prematurely for the following reasons:

- toxicity,
- disease progression,
- refusal to continue the trial,
- withdrawal of consent,
- patient lost to follow up,
- major protocol violation.

Where possible, patients who have discontinued their treatment prematurely will receive the same follow-up as other patients.

1.16 Unblinding procedure

Unblinding will be considered for a specific patient

- 1/ if he/she is not achieving response after first cycle of treatment (crossover) or
- 2/ in case of unexpected serious adverse event potentially related to the study drug. In case of an unexpected serious adverse event potentially related to the study drug, the investigator will request the sponsor to unblind the study. In all cases and until the procedure of unblinding has been fully discussed and completed, the drug/placebo should be suspended. If the unblinding is done, the patient will continue to be followed according to the protocol recommendations, including a potential premature discontinuation of treatment if appropriate.

1.17 Criteria for terminating the study

The trial can be suspended or terminated by the sponsor after consultation with the review Board (IRB), or other regulatory body for the following reasons:

- an unexpectedly high frequency and/or severity of toxicity,
- insufficient patient recruitment,
- insufficient quality of data collection.

1.18 Follow-up

1.18.1 Phase I:

Phase I patients will be followed up to 60 days after the last study drug administration in order to determine if any DLTs are attributable to Nintedanib. When counts have not recovered by day 60 and there is no morphological evidence of leukemia it is considered a Nintedanib associated hematologic DLT. Sixty days is the maximum length of time to wait for someone to recover before they are removed from the study.

Patients will then be followed every 3 months +/- 7 days for 24 months or until the patient begins receiving subsequent anti-cancer therapy or death, whichever comes first. The following information will be collected; first subsequent anti-cancer therapy (if applicable), documentation of last disease progression/relapse, and date of death. Patients or their caregivers will be contacted by phone.

1.18.2 Phase II:

Phase II patients will be followed every 3 months +/- 7 days for 24 months or until the patient begins receiving subsequent anti-cancer therapy or death, whichever comes first. The following information will be collected; Information regarding the first subsequent anti-cancer therapy (if applicable), documentation/date of last disease progression/relapse, and date of death. Patients or their caregivers will be contacted by phone.

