1.6 Definition of dose limiting toxicities (DLT) during phase I

In order to determine safety of the combination, all adverse events will be recorded on the case report forms and graded using the NCI CTC criteria (version 4.03). Toxicities not listed on the CTC will be graded as mild, moderate, or severe. The local Investigator, in consultation with the clinical staff caring for the patient, and the Protocol PI will determine the relationship to study drugs (unrelated, unlikely, possibly related, probably related, related). Dose limiting toxicity (DLT) will be either as specified below; for organ systems not included, DLT will also include any Grade III or IV non-hematologic toxicity thought possibly or probably related to study drug administration.

Specifically defined DLTs: Drug-related vomiting and nausea CTCAE grade \geq 2 for 5 or more consecutive days despite optimal supportive care. Drug-related diarrhea CTCAE grade \geq 2 persisting for 8 or more consecutive days despite optimal supportive care. Drug-related hypertension CTCAE grade \geq 3 despite optimal supportive care or intervention.

Drug-related transaminase elevation (ALT and/or AST) CTCAE grade \geq 3 or transaminase elevation CTCAE grade \geq 2 (ALT and/or AST) in conjunction with bilirubin CTCAE grade >1 . All other drug-related non-hematological toxicities of CTCAE grade \geq 3, except for isolated GGT increases. All other drug-related non-hematological toxicities of CTCAE grade 2 leading to an interruption of the BIBF 1120 treatment for \geq 14 consecutive days

Because all patients will be receiving cytarabine and idarubicin in conjunction with nintedanib, patients will not be evaluable for nintedanib- associated hematological toxicity.

Patients will have bone marrow assessed at physician's discretion by day 35 of treatment. If blood counts have not recovered, but marrow is free of morphologic evidence of leukemia, patients may be followed clinically until day 45. If counts have not recovered by day 60 and there is no morphologic evidence of leukemia, this will be considered a nintedanib- associated hematologic DLT.

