1.10.2 Evaluation during treatment period

The treatment period begins Cycle 1 Day 1 and can continue until up to 30 days after the last dose of Nintedanib. The treatment period can include a maximum of 2 (28 day) induction and 2 (28 day) consolidation cycles. If Maintenance therapy is indicated, patients will be followed monthly for the first 12 months and then every three months for the following year (a maximum of 24 months). Number and type of cycle will vary by patient and according to local SOC procedures.

Labs between day 8 and counts recovery can be done +/-2day

The following assessments need to be completed:

- Physical examination daily from day 1 to day 6 and then twice weekly during the induction cycle(s) 1 and 2 (if receiving a second cycle). During consolidation cycle(s) 1 and 2 at day 1, then weekly, and at the end of each cycle.
- ECOG performance status weekly during the first induction cycle and at the end of each cycle thereafter,
- Any adverse event,
- Concomitant medication,
- CBC with differential daily from day 1 to day 5 and then every other day for the first cycle and three times weekly of each cycle thereafter, (differential done as per hospital standard of care) entire panel required at response evaluation
- Serum chemistry daily from day 1-5. Then at a minimum of twice weekly, 3-4 days apart (+/- 2 days) during the first cycle and every other week each cycle thereafter. It includes AST, ALT, alkaline phosphatase, total bilirubin, BUN, serum creatinine, glucose, calcium, sodium, potassium, chloride, bicarbonate, total protein, albumin, LDH and magnesium
- Pregnancy test prior the beginning of each new treatment cycle (women of childbearing potential only)
- Coagulation profile daily from Day 1-5 of cycle 1 and then weekly during the first two cycles: prothrombin time, activated partial-thromboplastin time, fibrinogen,
- Bone marrow evaluation will be performed in patients with complete clearance of blasts in the blood on Day 14 (+/- 1 day) and at the end of cycle 1 Day 28 (+/- 7 days) and decided by local investigator based on count recovery. Threshold: ANC at 1 and PLT at 50,
- Assess LVEF before cycle 2; this can be done any time after Cycle 1 day 14 up to the start of cycle 2, ideally closer to cycle 2 Day 1 using 3D Echocardiogram or the biplane Simpson method.

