1.10.4 End of study treatment evaluation

A clinical work-up is to be performed at the end of treatment with Nintedanib within 30 days after the last administration of Nintedanib:

- Complete physical examination,
- Weight,
- ECOG performance status,
- Vital signs,
- Any adverse event,
- EKG,
- Assess LVEF, using 3D Echocardiogram or the biplane Simpson method, after Cycle 1 EOT visit ONLY
- Concomitant medication,
- Hematology: CBC with differential and hemoglobin,

- Serum chemistry including AST, ALT, alkaline phosphatase, total bilirubin, BUN, serum creatinine, glucose, calcium, sodium, potassium, magnesium, chloride, bicarbonate, total protein, albumin, and LDH
- Bone marrow evaluation will be performed in patients with complete clearance of blasts in the blood,
- Pregnancy test up to 3 months after last dose of Nintedanib (women of childbearing potential only)
- Pharmacodynamic assessment: collection of blood (5 x 4mL) and bone marrow samples (5-6 mL if a bone marrow aspirate is performed).

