1.19.9 Reporting to Boehringer Ingelheim

Upon inclusion into a trial, the patient's condition is assessed (e.g. documentation of history / concomitant diagnoses and diseases), and relevant changes from baseline are noted subsequently.

All adverse events, serious and non-serious, that occur from the time of signing the informed consent through 30 days following cessation of Nintedanib will be collected and documented by the investigator.

The Yale Project Manager shall report all SAEs and non-serious AEs which are relevant to a reported SAE by fax using BI's SAE form to BI Unique Entry Point as detailed below in accordance with the following timelines:

- within five (5) calendar days upon receipt of initial and follow-up SAEs containing at least one fatal or immediately life-threatening event;
- within ten (10) calendar days upon receipt of any other initial and follow-up SAEs.

Boehringer Ingelheim Pharmaceuticals, Inc.

[name]

[name]

[contact]

For each adverse event, the investigator will provide the onset date, end date, intensity, treatment required, outcome, seriousness, causal relationship and action taken with the investigational drug.

The investigator will also determine the expectedness of each AE based on the listed adverse event section of Boehringer Ingelheim's (BI's) Investigator Brochure for the Product.

The investigator does not need to actively monitor patients for adverse events once the clinical trial has ended. However, if the investigator becomes aware of an SAE(s) that occurred after the patient has completed the clinical trial (including any protocol specified follow-up period/Residual effect period), it should be reported to the PM if investigator considers it as relevant to the study drug. The PM will report to BI as required.

1.19.10 *Follow-up of SAEs*

The investigator is responsible for providing appropriate medical follow-up for patients until the event has resolved or stabilized or until the patient's death. Sometimes this may mean that follow-up will extend beyond the patient's withdrawal from the trial.

The investigator shall send additional information to the Project Manager and Sponsor PI using the SAE report form provided at start-up specifying that this is a follow-up report and not an initial report) within 48 hours of receiving the information. The investigator must also send the final follow-up once the SAE has resolved or stabilized.

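### Phase I judges DLTs over 60 days after the last dose, but planned adverse-event collection and visits end at 30 days

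*Combined protocol and SAP*

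**What the plan says.** The protocol gives several periods that bear on when a Phase I DLT can be seen.

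- **DLT period.** Section 1.18.1, echoed in the trial summary: "Phase I patients will be followed up to 60 days after the last study drug administration in order to determine if any DLTs" stem from nintedanib. Three-monthly telephone follow-up comes after that, and records "first subsequent anti-cancer therapy (if applicable), documentation of last disease progression/relapse, and date of death".
- **Adverse-event collection.** Section 1.19.9 covers "All adverse events, serious and non-serious, that occur from the time of signing the informed consent through 30 days following cessation of Nintedanib".
- **Treatment period.** Section 1.10.2 says that it "can continue until up to 30 days after the last dose of Nintedanib".
- **Last scheduled work-up.** Section 1.10.4 places it "within 30 days after the last administration of Nintedanib".
- **Hematologic DLT.** Section 1.6 applies "If counts have not recovered by day 60 and there is no morphologic evidence of leukemia". Section 1.5.1 counts its 60-day limit for count recovery from Cycle 1 Day 1, whereas section 1.18.1 counts its 60 days from the last dose.
- **One cycle.** The Phase I objective in section 1.3.1 refers to one cycle, and section 1.20.2 treats the safety evaluation as complete after one cycle.

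The study calendar (section 1.25.7) has an end-of-treatment column and a three-monthly follow-up column. It has none for study day 60 or for days 31 to 60 after the last dose. The Phase II dose is accepted if fewer than 2 of 6 patients have an attributable DLT (sections 1.6 and 1.7). The safety review committee must meet at least once after the first six patients are included (section 1.20.3.2); completed DLT follow-up is not a condition.

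**The concern.** A DLT count is only as complete as the data behind it. If the protocol judges DLTs over 60 days but plans to collect the events for only 30, an event in the second half that meets the definition can be absent from the record and counted as no DLT. With six patients and a limit of one DLT, a single missed patient can turn 2/6 into 1/6 and carry the higher nintedanib dose into the randomized phase. Because the periods differ in length and in starting point, two careful readers could also count DLTs differently from the same patients.

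**Working it through.** **Calendar arithmetic.** Inputs: last cycle 1 dose on day 28 (section 1.5.1); collection to 30 days after nintedanib (1.19.9); DLT period to 60 days after the last dose (1.18.1); count reading at day 60 from Cycle 1 Day 1 (1.5.1, 1.6).

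- Collection closes: 28 + 30 = day 58.
- DLT period closes: 28 + 60 = day 88.
- Gap: 88 − 58 = 30 days.
- Count reading: 60 − 28 = 32 days after the last dose, so 32 − 30 = 2 days after collection closes.
- With the optional day 8 marrow, the last dose is on the morning of day 29. The dates become day 59 and day 89, and the count reading falls 1 day after collection closes.
- If nintedanib stopped on day 15 (an example), collection closes on 15 + 30 = day 45, which is 60 − 45 = 15 days before the count reading.

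**What can fall in the gap.** Section 1.6 makes any possibly or probably related grade 3-4 non-hematologic toxicity a DLT, and the event need not be serious. Section 1.19.6 keeps related serious events reportable without limit, but not non-serious ones. It ties reporting of adverse events of special interest to the same 30 days. Section 1.19.7 follows liver abnormalities already found; it does not schedule a test to find one.

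**Effect on the gate.** The protocol states no operating characteristics for this rule, so there is no figure to reproduce. Let p be the true DLT rate and f the share of patients with a DLT whose only DLT goes unrecorded. The documents give neither, so both are assumptions. The chance of passing is

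P(pass) = (1 − q)^6 + 6q(1 − q)^5, with q = p(1 − f).

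For p = 0.20 and f = 0: 0.8^6 + 6 × 0.2 × 0.8^5 = 0.2621 + 0.3932 = 0.6554 (unrounded sum 0.65536).

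| p | f = 0 | f = 5% | f = 10% | f = 20% |
|---|---|---|---|---|
| 0.10 | 0.8857 | 0.8954 | 0.9048 | 0.9227 |
| 0.20 | 0.6554 | 0.6799 | 0.7044 | 0.7528 |
| 0.33 | 0.3578 | 0.3915 | 0.4267 | 0.5010 |

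Since q cannot exceed p, missed DLTs can only raise the chance of passing. At p = 0.33 the rise is 3.4, 6.9 and 14.3 percentage points for the three values of f; at p = 0.20 it is 2.5, 4.9 and 9.7.

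**The case against.** The strongest reply is that the protocol captures more than the 30-day limit suggests.

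- Section 1.18.1 is the Phase I rule for exactly this period, and its telephone calls follow the 60 days; they do not replace days 31 to 60.
- Section 1.6 says, without a time limit, that all adverse events go on the case report forms, and the calendar footnotes have them assessed on an ongoing basis.
- Related serious events after 30 days must be reported.
- Patients who go on to a second cycle, consolidation or maintenance remain under collection.

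A late first event also looks uncommon: section 1.14.1 gives a half-life of 7 to 19 hours and describes grade 3 liver enzyme rises in phase II as early and reversible.

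Most of this stands, and it rules out three stronger readings that a reader might draw.

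- *Slow DLTs are lost.* Events that start within 30 days are recorded with start and end dates. The gastrointestinal DLTs need 5 or 8 days, and the general grade 2 DLT needs a nintedanib interruption of at least 14 days, so it cannot first arise long after the final dose.
- *Unrecovered counts have no data source.* The day-60 rule requires a count, and section 1.10.2 implies laboratory tests until recovery. What is missing is the calendar entry and agreement with the adverse-event window.
- *Late DLTs are never recorded.* Related serious ones are.

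The reply does not supply a planned visit, laboratory test or collection rule that would find a new non-serious DLT 31 to 60 days after the last dose. An intention to follow patients is not a collection schedule, and section 1.19.9 gives an explicit end date for non-serious events.

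**Conclusion.** The point holds as a conflict between the stated DLT period and the planned data collection. It is confined to patients who receive no further study treatment after cycle 1. For them, up to 30 days of the stated DLT period lack planned capture of new non-serious related grade 3-4 non-hematologic events. The day-60 count is unscheduled and falls 1 or 2 days after collection closes following a full cycle, and earlier stopping widens that interval.

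The direction of any error is certain: toward passing. Its size is not known. The table rests on assumed values of p and f, and f is probably small given the pharmacology that the protocol itself describes. A reader might infer that the Phase I gate is materially biased; the documents do not support that. They show a gap that could matter in a six-patient decision and that is inexpensive to close.

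**What to change.** Reconcile sections 1.3.1, 1.5.1, 1.6, 1.10.2, 1.10.4, 1.18.1, 1.19.9 and 1.20.2 into one Phase I DLT window with one start point. Which length is right is for the sponsor to settle. Then:

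1. Tie the window to cycle 1. A window that runs from the last study drug could stay open through maintenance, which may last two years, and hold up the gate. State how patients who start cycle 2 before the window closes are counted.
2. Collect all adverse events, blood counts and chemistry to the end of that window, including the day-60 count that section 1.6 already needs, whenever nintedanib stopped.
3. Add the assessment to the study calendar.
4. Have the safety review committee count DLTs only when each of the six patients has completed the window or has had a DLT. Two patients with a DLT settle the gate at once, so only a pass has to wait.

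The cost is one amendment, one extra assessment for 6 to 12 patients, and a short delay. Counted from the sixth patient's day 28, the wait would be 60 − 28 = 32 days if the window closed on day 60, and 88 − 28 = 60 days if it closed on day 88.

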1.1 Trial summary

Title	A phase I-II trial of a combination of Nintedanib, an oral VEGF inhibitor, in combination with induction chemotherapy for patients with refractory or first relapse acute myeloid leukemia
Indication	Treatment of patients with relapsed/refractory AML as defined by the WHO
Design	Phase I- randomized II study
Sponsor	YALE UNIVERSITY
Contact	[name] PhD [contact] [contact] Email: [contact]
Products	Nintedanib/ placebo, idarubicin, cytarabine
Summary of Rationale	Nintedanib is an oral VEGF inhibitor with a good tolerance profile. There is evidence of a potential clinical impact of VEGF inhibition in AML and some in vitro evidence of activity of Nintedanib against AML blasts. Given that outcome of relapse/refractory AML patient is poor and that no standard option is available for this group of patients, we anticipate that a combination of nintedanib+ induction chemotherapy may be an effective strategy for this group of patients.
Treatment plan	
Phase I: Patients who meet eligibility criteria and sign informed consent will receive the following during an inpatient hospital stay; Idarubicin 12mg/m²/d IV Push over 10-15 minutes days 1 to 3, cytarabine 0.667g/m²/d (24 hr.) IV infusion day 1 to 3 and Nintedanib 200mg BID PO day 8-28. There will be no drug administered on days 4-7. Length of inpatient hospital stay is based on local site SOP.
 
Phase II: Patients who meet eligibility criteria and sign informed consent will receive the following during an inpatient hospital stay; Idarubicin 12mg/m²/d IV Push over 10-15 minutes days 1 to 3, cytarabine 0.667g/m²/d (24 hr.) IV infusion day 1 to 3 and Nintedanib 200mg BID PO on day 8-28 OR placebo. There will be no drug administered on days 4-7. Length of inpatient hospital stay is based on local site SOP.
 
For both Phase I and II, a maximum of 2 induction and 2 consolidation cycles may be given, cycles are 28 days.
 
During Phase II, all Patients failing to achieve response based on IWG 2003 AML response criteria after cycle 1 will be unblinded, and all those who had been receiving placebo will be offered Nintedanib+ chemotherapy (cross over) for cycle 2. Patients in the Nintedanib arm can be given a second cycle of Nintedanib.
 
Nintedanib maintenance treatment will be given to responding pts not eligible for Hematopoietic stem cell transplantation (HCT) for up to two years or until disease progression. Patients eligible for HSCT will be taken off study prior to HSCT.

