1.4.2 Secondary endpoints

Overall response rate will be defined according to IWG 2003 criteria⁴⁶ and includes: CR, CRp, CRI, PR, and marrow leukemia free state (MLFS). Rates of hematological improvements (as defined by IWG 2006 Myelodysplastic syndromes criteria⁴⁷) will also be recorded.

Overall Survival will be defined from time of treatment initiation to the time of last follow-up or death. Survival with censoring patients at the time of transplantation will also be evaluated.

Leukemia free survival will be defined from time of documentation of complete remission (CR+CRp+CRI) to the time of last follow-up, relapse, or death of any cause. Survival with censoring patients at the time of transplantation will also be evaluated.

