Phase II: Based on the phase I dose, in the randomized phase II, the combination of chemotherapy + Nintedanib will be compared with chemotherapy+placebo. The AML chemotherapy induction and consolidation regimen occur at an inpatient hospital stay typically averaging 5 weeks and is Standard of Care (SOC) per local hospital policy. The induction and consolidation chemotherapy regimen for Phase II are identical to that in Phase I and combines Idarubicin 12mg/m²/d IV push over 10-15 minutes days 1 to 3 and Cytarabine 0.667g/m²/d (24 hr. IV infusion) day 1 to 3. In Phase II, patients will be randomized to receive the combination chemotherapy in addition to Nintedanib (dose determined in Phase I) at Day 8 through day 28 (end of cycle) or placebo at Day 8 until day 28 (end of cycle). Patients may be discharged based on local SOC and re-admitted prior to the start of the next cycle however, some patients will stay in the hospital continuously (especially between the first two induction cycles). Induction cycle 2 can begin as early as study day 29 regardless of count recovery status if the investigator believes it would be clinically beneficial. Patients can be given a “break” between cycles of induction based on investigator’s clinical judgement and clinical response. Count recovery is necessary before a consolidation cycle can begin. If count recovery is not achieved 60 days after Cycle 1 Day 1, the patient is removed from the study. **Figure 2.** describes the overall

strategy of the Phase II portion of the study. All patients will be evaluated for response based upon count recovery or following day 45, whichever comes first. Patients without count recovery and without signs of bone marrow leukemia at day 45 will be followed up to day 60. If no recovery is observed at day 60, patients will be removed from protocol and considered a failure.

In phase I, patients who fail to achieve CR or CRp based on IWG 2003 AML response criteria (pg. 77) after first cycle of treatment may receive a second cycle of treatment using Nintedanib+ chemotherapy. Patients who achieve CR or CRp after one or two induction cycles may receive up to 2 cycles of consolidation using the same regimen.

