In phase II, patients failing to achieve response based on IWG 2003 AML response criteria after cycle 1 will be unblinded, and all those who had been receiving placebo will be offered a cycle of Nintedanib+ chemotherapy (cross over). Patients in the Nintedanib arm may receive a second induction cycle of Nintedanib. Based on clinical judgement, patients can receive up to 2 cycles of consolidation after induction cycle (s) are complete.

Patients are eligible for allogeneic transplantation as soon as remission is achieved and a donor is identified. All transplant procedures occur off study. For responding patients not eligible for transplantation, maintenance therapy with Nintedanib/Placebo will be provided until documented progression.

Patients should NOT start Cycle 1 day 1 on a Thursday or Friday in order to facilitate sample collection, processing and shipment to Sponsor to avoid weekend deliveries.

[figure not shown]

Figure 2. Global treatment strategy of the Phase II portion of the study

NIN/PLA: Nintedanib/ Placebo, CR: complete response, CRp: CR with incomplete counts recovery. Patients can receive up to 2 induction and 2 consolidation cycles.

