1.19 Serious Adverse events

1.19.1 General definition

An adverse event (AE) is any expected or unexpected harmful and unintended occurrence or exacerbation in a clinical trial subject, whether or not related to the trial or the investigational product. It can be a new intercurrent disease, exacerbation of a concomitant disease, an accident, or any other deterioration in the patient's health, including abnormal laboratory findings. All AEs will be reported from the time that consent is obtained.

Any medical condition that existed before the start of the study treatment and that remains unchanged or improves must not be recorded as an AE. If a medical condition worsens, it must be recorded as an AE. The diagnosis or syndrome rather than the individual signs or symptoms must be recorded on the AE pages of the case report form.

An event is considered a serious adverse event (SAE) if it:

- Results in death; Death due to disease progression is excluded
- Is life-threatening,
- Requires inpatient hospitalization or prolongation of existing hospitalization,
- Cause any persistent or significant disability/ incapacity,
- Causes a congenital anomaly, birth defect or abortion,
- Is a new cancer (that is not the condition of the study)
- Is associated with an overdose
- Is another medically significant event

The terms *disability* and *incapacity* refer to any clinically significant physical or mental handicap, whether temporary or permanent, that affects the patient's physical activity and/or quality of life.

A *medically significant* event is any clinical event or laboratory finding considered by the investigator to be serious that does not meet the seriousness criteria defined above. It may pose a risk to the patient and require medical intervention to prevent one of the serious outcomes mentioned previously (e.g. *an overdose, second cancer, pregnancy, and new information can be considered medically significant*).

The following are not considered as serious adverse events:

- Death due to disease progression
- Hospitalization for < 24 hours
- Hospitalization scheduled before the start of the trial and/or stipulated in the protocol (e.g. for biopsy or chemotherapy)

The AE pages of the case report form and an SAE form should be completed for each AE considered serious.

For each AE, the investigator shall provide information about the intensity, start and end dates, causality, the action taken, and the outcome

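### Follow-up stops at the first subsequent anti-cancer therapy, so later deaths are not collected and overall survival is informatively censored, by an amount and in a direction the documents do not fix

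*Combined protocol and SAP*

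**What the plan says.** **Endpoint.** Section 1.3.2 makes OS a secondary objective, compared between nintedanib and placebo. Section 1.4.2 states: "Overall Survival will be defined from time of treatment initiation to the time of last follow-up or death". It then adds a second analysis: "Survival with censoring patients at the time of transplantation will also be evaluated".

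**Follow-up.** The synopsis (1.1, Patient follow-up) and Sections 1.18.1 and 1.18.2 set contact every 3 months for 24 months, "until the patient begins receiving subsequent anti-cancer therapy or death, whichever comes first". Date of death is one of the items collected at those contacts.

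**Transplant.** The synopsis says: "Patients eligible for HSCT will be taken off study prior to HSCT". Section 1.5.1 says: "All transplant procedures occur off study". Neither says whether HSCT is a subsequent anti-cancer therapy, or whether vital status is sought afterwards.

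**Calendar.** The follow-up column in 1.25.7 lists date of death every 3 months up to 2 years and does not repeat the stop at next therapy.

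**The concern.** Read together, 1.4.2 and 1.18 censor OS on the day next therapy starts. In relapsed or refractory AML that start usually follows non-response or relapse, and HSCT follows remission. Patients who leave the risk set therefore differ in prognosis from those who stay, and a Kaplan-Meier curve that treats the two groups as exchangeable estimates neither survival over the whole treatment course nor any other defined quantity. That the censoring is informative is an inference from why these treatments are started; the documents do not state it.

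There is also a conflict over transplant. Offering the HSCT-censored analysis as an addition implies that the main OS analysis includes deaths after HSCT. If HSCT triggers the stop, the two analyses coincide for every transplanted patient.

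Many patients could be affected. Section 1.7 plans on CR rates of 15% and 40%, so 60% to 85% of patients are expected not to reach CR after cycle 1, although some then receive a second cycle on protocol.

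**Working it through.** **1. Does another section recover the deaths?**

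| Section | What it provides | Recovers deaths after next therapy? |
|---|---|---|
| 1.15 | "patients who have discontinued their treatment prematurely will receive the same follow-up as other patients" (where possible) | No: the same stop applies |
| 1.19.1 | SAE for death, but "Death due to disease progression is excluded" | Not progression deaths |
| 1.19.6 | SAEs to 30 days after last study drug; later ones only if considered related | Few |
| 1.5.1 | "If no recovery is observed at day 60, patients will be removed from protocol and considered a failure" | Silent on vital status |
| 1.25.7 | Date of death to 2 years, no stop stated | Unclear; differs from 1.18 |

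None clearly requires contact after next therapy.

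**2. Inputs.** The plan has no OS figure to reproduce: no hazard ratio, event target or expected share starting next therapy. From the documents: CR 15% and 40%, at most 24 patients per arm (last row of the table in 1.7), 24 months of follow-up, and a median OS of at most 6 months in the background text (1.2.1). All other inputs are assumptions: exponential survival with median 4 months in non-responders and 14 months in responders; a share *s* of non-responders starting next therapy at 1.5-2.5 months, or at 3-4 months (after a second protocol cycle).

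**3. Deaths lost among non-responders (hazard unchanged by next therapy).**

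Share lost = *s* × [S(c) − S(24)] / [1 − S(24)], with S(t) = 2^(−t/4) and c the midpoint of the start window.

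- S(2) = 0.707, S(3.5) = 0.545, S(24) = 0.016.
- Start at 1.5-2.5 months: *s* × 0.691/0.984 = 0.70*s*. For *s* = 20/40/60/80% this is 14/28/42/56%.
- Start at 3-4 months: *s* × 0.530/0.984 = 0.54*s*, or 11/22/32/43%.

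**4. Error in 12-month OS.** True OS with unchanged hazard and no HSCT, at CR 15%: 0.15 × 2^(−12/14) + 0.85 × 2^(−12/4) = 0.083 + 0.106 = 18.9%. The censored Kaplan-Meier estimate tends to exp(−∫h dt), where h = Σ wλSG / Σ wSG over the patient groups, with w the group's share, λ its hazard, S its survival and G its probability of not yet being censored. Removing non-responders leaves the risk set enriched with responders, so h is too low even when next therapy changes nothing.

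Simulation with 200,000 patients per scenario (start at 1.5-2.5 months in all four rows; HR is the hazard ratio after the event):

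| CR | Non-responders starting next therapy | HR after next therapy | Responders to HSCT (censored) | True | Estimated | Error (points) |
|---|---|---|---|---|---|---|
| 15% | 80% | 1 | none | 18.9% | 29.5% | +10.6 |
| 15% | 60% | 0.5 | none | 27.8% | 24.5% | −3.3 |
| 40% | 60% | 1 | 50%, HR 0.5 | 32.0% | 32.3% | +0.3 |
| 40% | 40% | 0.5 | 50%, HR 0.5 | 36.4% | 29.0% | −7.4 |

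Evaluating the limit formula numerically gives the same four errors to within 0.2 points.

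The full grid has 96 scenarios: two CR rates, four values of *s*, two start windows, HR 1 or 0.5 after next therapy, and HSCT censoring of no responders, or of half at 2-5 months with HR 1 or 0.5. Errors run from −8 to +11 points at CR 15% and from −8 to +12 at CR 40%.

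| Branch | Scenarios | High by >1 point | Low by >1 point | Within 1 point |
|---|---|---|---|---|
| No HSCT censoring | 32 | 20 | 6 | 6 |
| Half of responders censored at HSCT | 64 | 11 | 43 | 10 |
| All | 96 | 31 | 49 | 16 |

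These are counts of grid cells, not probabilities, and one or two cells near the 1-point cut move between reruns. Without HSCT censoring the range is −3 to +12. Widening the HR after next therapy to 0.3-1.5 there gives −9.4 to +15.8 at CR 15% and −3.2 to +15.2 at CR 40%.

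**5. A second model.** One hazard before next therapy, true median 6 months, 48 patients (24 per arm), a share starting next therapy of 30%, 50% or 70%, and hazard ratio *k* after it.

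- Observed deaths fall from about 42-47 with full follow-up to 32-33, 23-24 and 14.
- At 50%, the estimated median is 4.9, 6.0, 7.3 and 8.7 months for *k* = 0.5, 1, 2 and 4. Over all settings it runs from 4.1 to 10.9. Here *k* = 1 gives no bias, only lost deaths.
- Between arms with equal true medians and *k* = 2, if 30% of the nintedanib arm and 60% of the placebo arm start therapy, the hazard ratio moves from 0.95 to 1.16. With the shares reversed it moves from 1.06 to 0.87.

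**6. Scale.** The standard error of a 30% 12-month OS with 24 patients is √(0.3 × 0.7/24) = 0.094, about 9 points.

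**The case against.** - **The calendar may rescue the deaths.** It lists date of death to 2 years with no stop at next therapy. But it does not say contact continues, and the synopsis, 1.18.1 and 1.18.2 say it ends. At best this is a conflict to reconcile.
- **The OS definition is consistent with the stop.** OS runs to last follow-up, and 1.18 says when that is. This stands: for next therapy the objection is to a design choice, not to a contradiction. The conflict lies with the calendar and with the added HSCT-censored analysis.
- **The low side leans on HSCT.** Of the 49 low scenarios, 43 assume that HSCT ends follow-up, which the plan does not say. This too stands, but 6 low scenarios remain without that premise, so the sign is still open.
- **The high extreme is demanding.** Errors of +11 to +12 need 80% of non-responders to start off-protocol therapy by 2.5 months with unchanged hazard, although a second cycle on protocol is offered. With a start at 3-4 months the maximum is about +9. The model also leaves out relapsing responders who start new therapy.
- **Practical weight is limited.** OS is secondary, Section 1.7 does not power a comparison of arms, only 2 of the 96 errors exceed one standard error, and the median absolute error is about 3 points. Crossover of placebo non-responders confounds between-arm OS anyway. All of this is true and limits the severity, but OS will still be reported, and deaths not collected may be unrecoverable later.

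**Conclusion.** The concern holds. Followed as written, the plan stops seeking deaths at a point that depends on prognosis, and no other section clearly makes up for it. That reading of the text is firm.

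The size is not. It rests on assumed survival, assumed uptake and timing of next therapy, and an assumed hazard afterwards. Within the main grid, 12-month OS is wrong by −8 to +12 points, or −3 to +12 if HSCT does not end follow-up. The quantities needed to determine or correct the error are those the plan stops collecting.

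The primary endpoint (CR/CRp after cycle 1) is untouched. This should be fixed, but it does not threaten the main conclusion of the trial.

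**What to change.** - **Synopsis (Patient follow-up), 1.18.1 and 1.18.2:** collect vital status every 3 months to 24 months or death, regardless of subsequent anti-cancer therapy, HSCT or removal from study. Record the dates of next therapy and of HSCT.
- **Same sections:** state whether HSCT counts as subsequent anti-cancer therapy.
- **1.4.2:** make OS without censoring at next therapy or HSCT the main OS analysis, and keep the HSCT-censored version as supportive.
- **1.25.7:** align the follow-up column with the revised text.

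The cost is wording in these places and a few extra calls per patient. Quarterly phone contact already exists, and 24 months allows at most 24/3 = 8 calls. Consent wording may be needed for contact after a patient leaves the study. Treatment is unchanged. The change does not remove the confounding from crossover, which should be acknowledged when OS is compared between arms.
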